The DF/HCC Sponsor will review all final audit reports and corrective action plans, if applicable. The Coordinating Center, must forward any reports to the DF/HCC ODQ per DF/HCC policy for review by the DF/HCC Audit Committee. For unacceptable audits, the DF/HCC Audit Committee would forward the final audit report and corrective action plan to the DFCI IRB as applicable.

Participating Institution Performance

The DF/HCC Sponsor and the IRB of record are charged with considering the totality of an institution's performance in considering institutional participation in the protocol.

Participating Institutions that fail to meet the performance goals of accrual, submission of timely and accurate data, adherence to protocol requirements, and compliance with state and federal regulations, may be recommended for a six-month probation period. Such institutions must respond with a corrective action plan and must demonstrate during the probation period that deficiencies have been corrected, as evidenced by the improved performance measures. Participating Institutions that fail to demonstrate significant improvement will be considered by the DF/HCC Sponsor for revocation of participation. A DF/HCC Sponsor and/or the DFCI IRB may terminate a site's participation if it is determined that a site is not fulfilling its responsibilities as described above.

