4.0 Planned Enrollment

This study aims to enroll a total of 40 participants as follows:

Pilot RCT DFCI and UAB: The target sample size is 40 participants. At DFCI, a total of 28 participants will be enrolled and randomized (thus 14 participants will receive PediCARE and 14 participants will receive UC). At UAB a total of 12 participants will be enrolled and randomized (thus 6 participants will receive PediCARE and 6 participants will receive UC).

Families will be recruited consecutively at each site over a 6-month time period. Patients will be randomized 1:1 to PediCARE versus Usual Care (UC) and randomization will be stratified by site.

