6.0 Multi-Site Research

6.1 Study Team:

DFCI will serve as the lead site for PediCARE and the single IRB of record for this small, pilot feasibility intervention study. The Study Team at each site will participate in monthly study phone calls to address (a) accrual rate, (b) study eligibility determination issues, (c) data completion rates including conformance with informed consent requirements, (d) intervention fidelity indicators, (e) adverse events, and (f) compliance with data management procedures.

6.2 Collaborating Sites and Role of Sites in Performing Proposed Research:

This study will be conducted at both DFCI and University of Alabama Birmingham Children's of Alabama (UAB). Inclusion of UAB as a collaborating site in this pilot study will leverage patient catchment areas which include both New England and Southern states to recruit a more diverse patient population from the perspective of race, ethnicity, geography and culture—particularly meaningful in the context of poverty as a social determinant of health. Furthermore, pilot feasibility at diverse sites will inform subsequent scalability of our approach for a multi-center RCT intervention study to definitively evaluate the impact of PediCARE on childhood cancer outcomes.

Under the direction of the site PI [name], UAB will recruit and enroll a total of 12 participants in study. Participants will be randomized to receipt of PediCARE or UC. UAB will maintain a local

patient tracking database, communicate participant enrollment data to DFCI for central administration of randomization and intervention components; administer baseline and follow-up parent surveys; and transmit required source documentation to DFCI for central data monitoring.

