7.0 Study Timelines

New patients at each site are continuously identified by study teams. Eligible parents will be approached sequentially by study teams and offered an opportunity to participate following written informed consent. Participants who choose to enroll will be on study for 6-months.

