8.0 Study Endpoints

8.1 Feasibility: The primary endpoint of this study is feasibility. Feasibility will be defined as at least 75% consent to randomization and at most 20% attrition per arm. We will assess process barriers to feasibility including recruitment, attrition by arm and parent report of PediCARE component utilization (i.e. food and transportation).

[figure not shown]
Study Timeline (Months)	Months 1 -6 Year 1	Months 7- 12 Year 1	Months 1-6 Year 2
Screen and enroll families (6 months)			
Intervention administration (6 months)			
Data analysis			

8.2 HMM and Utilization: The secondary endpoints of this study will be used to generate effect size estimates to support planning of a subsequent RCT. Secondary endpoints will be evaluated comparing recipients of PediCARE versus Usual Care. Secondary outcomes include change in HMM utilizing an HMM score (range 0-4) at 6-months compared to baseline; and proportion of patients experiencing an Emergency Department (ED) visit or Intensive Care Unit (ICU) admission over 6-months.

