11.0 Statistical Considerations

Accrual: Annually, 420 new patients receive chemotherapy at DFCI and 120 at UAB. Based on prior institutional HMH data, we estimate 20% will be eligible to participate at DFCI (N=84) and 30% will be eligible to participate at UAB (N=36). We estimate a 75% consent rate for a total possible annual sample size of N=90 patients (63 DFCI, 27 UAB). Forty patients will be accrued over 6-months at DFCI (n=28) and UAB (n=12). Patients will be randomized 1:1 by site to PediCARE versus UC.

Analysis Plan: Sample demographic, disease, treatment and utilization variables from the survey instruments and medical chart will be described by summary statistics.

The rate of consent to randomized intervention and the 6-month completion will be estimated along with a 90% confidence interval (CI). Feasibility will be established if the upper bound of the CI contains 75% and 80% for consent and follow-up respectively. With an estimated 60 eligible patients at 6 months, at least 39 (65%; 90% CI 53.6-75.2%) need to enroll for the upper bound of the 90% CI contain 75%. With an estimated 40 randomized patients, at least 28 (70%; 90% CI 56.0-81.7%) need to have complete 6-month data to have the upper bound of the 90% CI contain 80%. The 6-month completion rate will also be estimated along with a 90% CI by randomized arm (PediCARE and UC).

For each family, the difference between 6-month and baseline HMH scores will be categorized as improved (change score <0) or not improved (change score ≥0). For each arm, the proportion of families with improved HMH at the completion of the intervention (6-months) will be estimated along with a 90% exact CI. Based on prior data, we assume a 30% resolution in HMH in UC, thus the 90% CI will be within ±24.9%. For each arm, the per patient number of ED visits and ICU stays will be summarized (median, range). The proportion of patients with at least one ED and/or ICU visit will be estimated for each arm, as well as the difference between arms, along with a 90% confidence interval. Additionally, the rate of HMH at the completion of the intervention pilot (6-months) along with a 90% exact confidence will be estimated for UC and PediCARE. For the PediCARE arm, the cost per patient, study team contact hours, and proportion with successful receipt of all intervention components will be described overall and by site.

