Participating institutions will be required to participate in monthly Coordinating Center initiated teleconferences.

Remote Monitoring will be performed by central monitoring of REDCap survey completion (data are electronically entered and stored thus source verification is non-applicable unless paper/pencil survey administered due to technological challenges in which case these will be scanned and securely emailed to DFCI for central data entry and source documentation).

Monitoring Reports

The DF/HCC Sponsor will review all monitoring reports to ensure protocol compliance. The DF/HCC Sponsor may increase the monitoring activities at Participating Institutions that are unable to comply with the protocol, DF/HCC Sponsor requirements or federal and local regulations.

Accrual Monitoring

Prior to extending a protocol to an external site, the DF/HCC Sponsor will establish accrual requirements for each participating institution. Accrual will be monitored for each participating institution by the DF/HCC Sponsor or designee. Sites that are not meeting their accrual expectations may be subject to termination.

Accrual expectations for University Alabama Birmingham are as follows: Enrollment of 12 participants over 12 months.

AUDITING: QUALITY ASSURANCE

Auditing is a method of Quality Assurance and involves the systematic and independent examination of all trial related activities and documents. Audits determine if evaluated activities were appropriately conducted and whether data was generated, recorded and analyzed, and accurately reported per the protocol, applicable Policies, and the Code of Federal Regulations (CFR).

DF/HCC Internal Audits

All Participating Institutions are subject to audit by the DF/HCC Office of Data Quality (ODQ). Typically, approximately 3-4 participants would be audited at the site over a 2-day period. If violations which impact participant safety or the integrity of the study are found, more participant records may be audited.

Audit Notifications

It is the Participating Institution's responsibility to notify the Coordinating Center of all external audits or inspections (e.g., FDA, EMA, NCI) that involve this protocol. All institutions will forward a copy of final audit and/or re-audit reports and corrective action plans (if applicable) to the Coordinating Center, within 12 weeks after the audit date.

Audit Reports

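### Does the 12-month accrual expectation for UAB in Appendix D undermine the 6-month enrolment plan?

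*Combined protocol and SAP*

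**What the plan says.** Section 4.0 gives the site target, "At UAB a total of 12 participants will be enrolled and randomized", and the recruitment window, "Families will be recruited consecutively at each site over a 6-month time period". Section 6.2 confirms that 12 is UAB's whole contribution: "UAB will recruit and enroll a total of 12 participants in study". The accrual paragraph of section 11.0 repeats the window together with the site split: "Forty patients will be accrued over 6-months at DFCI (n=28) and UAB (n=12"). The enrolment row of the timeline in section 8.0 is also labelled 6 months. Each family then has its own period of participation under section 7.0: "Participants who choose to enroll will be on study for 6-months".

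Appendix D, under Accrual Monitoring, states the expectation used to judge the collaborating site: "Accrual expectations for University Alabama Birmingham are as follows: Enrollment of 12 participants over 12 months". The same paragraph says that a site falling short may be terminated. The later paragraph on institutional performance lists accrual among several goals, allows a six-month probation, and asks for the site's performance to be judged as a whole.

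**The concern.** The same 12 families appear with two enrolment periods that differ by a factor of two, and the appendix does not call its figure a minimum. Time on study does not explain the gap, because the appendix sentence is about enrolment and the 6 months of participation are stated separately. On its face, UAB could recruit at half the planned pace and still satisfy the only accrual expectation written for it. In a pilot whose purpose is feasibility, that could mean a late finish, or a shortfall at the end of the planned window, with no formal trigger for action. A reader might also fear that a slow site would push the enrolled count below the 39 that section 11.0 requires.

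**Working it through.** **Inputs.** From section 11.0: 120 new chemotherapy patients a year at UAB, 30% eligible, 75% consent; 420 a year at DFCI, 20% eligible, same consent rate. From sections 4.0 and 11.0: 12 UAB and 28 DFCI enrolments in 6 months. From Appendix D: 12 UAB enrolments in 12 months.

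**Reproducing the plan's projection.**
- Eligible per year: 420 × 0.20 = 84 and 120 × 0.30 = 36.
- Consenting per year: 84 × 0.75 = 63 and 36 × 0.75 = 27, total 90, as stated.
- Eligible in 6 months: (84 + 36)/2 = 60, as stated, of whom 36/2 = 18 are at UAB.
- Exact 90% interval for 39/60: 53.6% to 75.2%, as stated.

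**The two paces.**
- Plan: 12/6 = 2 per month. Appendix D: 12/12 = 1 per month.
- Projected UAB yield: 27/12 = 2.25 per month, or 13.5 in 6 months. Twelve would be reached in 12/2.25 = 5.3 months, so the 6-month plan agrees with its own inputs.
- If UAB ran at exactly 1 per month, evenly spread, and DFCI reached 28, month 6 would show 6 + 28 = 34 of 40.

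**Does this reach the primary endpoint?** Section 8.1 defines feasibility by consent (at least 75%) and attrition (at most 20% per arm). Section 11.0 estimates both as proportions with 90% intervals. The 39 in section 11.0 is a count out of 60 eligible families. Setting 34 against a fixed 60 would treat every family not yet enrolled as a refusal. If UAB is slow because fewer eligible families present, the denominator falls as well. If it is slow because families decline, the consent rate itself records it. Neither case depends on the Appendix D line.

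**Is slow accrual visible otherwise?** Section 6.1 puts accrual rate first on the agenda of the monthly study calls. Appendix D has the monitoring committee follow accrual at each institution and meet quarterly, and gives the sponsor the same duty. Nothing ties these reviews to the 12-month figure.

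**What would a 12-in-6-months line do?** Take UAB to perform exactly as section 11.0 projects.
- Poisson arrivals with mean 13.5 (an assumption): P(fewer than 12) = 0.304, about 30%.
- Exactly 18 eligible, each consenting with probability 0.75 (an assumption): P(fewer than 12) = 0.139, about 14%.
- The existing line, Poisson with mean 27 over 12 months: P(fewer than 12) = 0.0004, below 0.1%.

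**The case for a change.** The best case for changing the text is that the appendix gives one expectation, attaches possible termination to it, and does not describe it as a floor beneath a faster plan. Sections 4.0, 8.0 and 11.0 all agree on 6 months, and section 11.0's projection supports them, so aligning the appendix would take one line. It can be added that 12 enrolments in 12 months are only 12/27 = 44% of the projected UAB yield, and that a 12-month window plus 6 months on study ends at month 18 rather than month 12.

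The textual point stands: the document never reconciles the two periods and does not show which was intended for the appendix. The rest carries less weight. The 27 is presented in section 11.0 as the total possible in a year, so it is a ceiling and not a commitment. The month-18 figure assumes that enrolment opens in month 1. Even then it falls within the 18 months that the section 8.0 table covers, though it would leave no time there for analysis after the last follow-up. Termination is discretionary. The one-line edit also has a cost: it would put a site that is performing as projected at a 14% to 30% risk of missing a line linked to termination, with a possible probation as long as the whole recruitment window.

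**Conclusion.** The inconsistency is genuine but administrative, and no change to the plan is needed. The recruitment plan and the site expectation do different jobs and can both be met. A performance line looser than the plan is ordinary practice, although the text does not prove that this was the intent. If the 12 months is a slip, the effect is the same: the sample size of 40, the 39-of-60 and 28-of-40 thresholds, the intervals and the feasibility definition do not use it. A shortfall at month 6 would come from actual recruitment and would be seen on the monthly calls and by the committee.

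The size of the mismatch is 1 against 2 families per month, or at most 6 families at month 6 if accrual is even and UAB only just keeps to the slower pace. Tightening the line offers no clear gain, given the 14% to 30% chance that an on-target site would miss it. That range rests on section 11.0's eligibility and consent rates and on the binomial and Poisson assumptions shown above.
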